
 Section 1.1, Synopsis Section 4.1.1, Screening and Enrollment Section 9.2, Sample Size Determination 	Specified that only Cohorts 1 and 2 have an intended minimum number of participants with evaluable data.	Optional Cohort 3 does not feature a safety review for purposes of moving to a subsequent cohort, and therefore does not have the same requirement for minimum participant numbers.

 Section 1.2 Schema 	Added a note to the schema to clarify that the LY:PBO ratio for Cohort 3 is an intention only.	As above.

 Section 6.1.1, Injection volumes and formulation concentrations 	Added a note to clarify that the number and volume of injections will be adjusted if any dose levels are modified.	Mistakenly omitted from earlier versions of the protocol.

 Section 10.3.3, Recording and Follow-Up of AE and/or SAE 	Removed reference to the Division of AIDS (DAIDS) table for grading AEs and SAEs.	The DAIDS table will not be used for this study.

 Section 11, References 	Removed DAIDS reference.	As above.

Table of Contents

1.	Protocol Summary	7
1.1.	Synopsis	7
1.2.	Schema.....	8
1.3.	Schedule of Activities (SoA)	9
2.	Introduction	15
2.1.	Study Rationale	15
2.2.	Background	15
2.2.1.	Summary Information from LY3819253 Program to Date	15
2.3.	Benefit/Risk Assessment	16
3.	Objectives and Endpoints.....	17
4.	Study Design	18
4.1.	Overall Design.....	18
4.1.1.	Screening and enrollment	18
4.1.2.	Inpatient stay	18
4.1.3.	Outpatient follow-up.....	19
4.2.	Scientific Rationale for Study Design	19
4.3.	Justification for Dose.....	19
4.4.	End of Study Definition.....	20
5.	Study Population	21
5.1.	Inclusion Criteria	21
5.2.	Exclusion Criteria.....	21
5.3.	Lifestyle Considerations	24
5.3.1.	Meals and Dietary Restrictions	24
5.3.2.	Caffeine, Alcohol, and Tobacco.....	24
5.3.3.	Activity	24
5.4.	Screen Failures	24
6.	Study Intervention.....	26
6.1.	Study Interventions Administered.....	26
6.1.1.	Injection volumes and formulation concentrations	27
6.1.2.	In the Event of a Retrospective Positive Sterility Finding from Prepared Study Intervention.....	27
6.2.	Preparation/Handling/Storage/Accountability	27
6.3.	Measures to Minimize Bias: Randomization and Blinding.....	28
6.4.	Study Intervention Compliance.....	28
6.5.	Concomitant Therapy	28
6.6.	Dose Modification	29
6.6.1.	Dose-Escalation Criteria	29

1.1. Synopsis

Protocol Title: A Randomized, Placebo-Controlled, Participant- and Investigator-Blind, Phase 1 Study to Evaluate the Pharmacokinetics, Safety, and Tolerability of LY3819253 Administered Subcutaneously to Healthy Participants

Short Title: A Randomized, Placebo-Controlled, Phase 1 Study to Evaluate the Pharmacokinetics, Safety, and Tolerability of LY3819253 Administered Subcutaneously to Healthy Participants

Rationale: The clinical program for LY3819253 so far has involved IV dosing of LY3819253. Study PYAG will investigate SC dosing of LY3819253. Single SC doses of LY3819253, 350 mg and 700 mg, will be administered to establish the PK, safety, and tolerability profiles in healthy participants.

Objectives and Endpoints

Objectives	Endpoints
Primary	
To determine the PK of single SC doses of LY3819253 in healthy participants	AUC(0-∞)
Secondary	
To describe safety and tolerability following single SC doses of LY3819253 in healthy participants	Incidence of spontaneously reported AEs, TEAEs, and SAEs; vital signs; clinical laboratory results
Exploratory	
To assess ISRs following single SC doses of LY3819253 in healthy participants	Characterization and measurement of incidence and severity of ISRs, including injection site pain, using data collected from the ISR assessment, and the exploratory tool (Scarletred)
To determine the immunogenicity of LY3819253 following single SC doses in healthy participants	Incidence of TEADA

Abbreviations: AE = adverse event; AUC(0-∞) = area under the concentration versus time curve from time 0 to infinity; ISR = injection site reaction; PK = pharmacokinetics; SAE = serious adverse event; SC = subcutaneous; TEADA = treatment-emergent antidrug antibodies; TEAE = treatment-emergent adverse event.

Overall Design

This is a single-site study in healthy participants who will receive a single SC dose of LY3819253. The study will be participant- and investigator-blinded, randomized, and placebo controlled.

Disclosure Statement: This is a PK and safety study to test LY3819253 and placebo in up to 3 dose cohorts.

Number of Participants:

[figure not shown]
A maximum of 36 participants will be enrolled to study intervention, with the intention that at least 6 participants randomized to LY3819253 have sufficient evaluable data in each of Cohorts 1 and 2.

Intervention Groups and Duration:

This is a single-dose study with an estimated duration for each participant of up to 16 weeks from screening through follow-up.

Data Monitoring Committee: No

1.2. Schema

Abbreviations: LY = LY3819253; PBO = placebo; SC = subcutaneous.

Note: The LY:PBO ratio for the optional Cohort 3 is an intention and may change subject to enrollment numbers. The planned dose for Cohort 3 may change based on data review during the study.

1.3. Schedule of Activities (SoA)

Procedure / Assessments	Screening	Treatment Period								Follow-up Visits				Comment
Visit Number	V1	V2								V3	V4	V5	V6/ ED	
Week(s)		0								2	4	8	12	
Study Day	-14 to -1	-1	1	2	3	4	5	6	7	15 ±2d	29 ±3d	60 ±3d	85 ±3d	
Informed consent (written)	X													
Review/confirm I/E criteria	X	X												After screening, ensure participants continue to meet I/E criteria.
Medical history including pre-existing conditions	X													
Weight/height	X												X	Height at screening only.
Urinalysis	X								X					
COVID-19 clinical screening	X	X								X	X	X	X	Symptoms and recent contact (see Section 5.2 for a description of symptoms and close contact). At designated timepoints and as needed during the study.
SARS-CoV-2 serology		X								X	X	X	X	Serology results are not needed before dosing.

Procedure / Assessments	Screening	Treatment Period								Follow-up Visits				Comment
	Visit Number	V1	V2								V3	V4	V5	
Week(s)		0								2	4	8	12	
Study Day	-14 to -1	-1	1	2	3	4	5	6	7	15 ±2d	29 ±3d	60 ±3d	85 ±3d	
SARS-CoV-2 point-of-care test	X	X												Additional point-of-care tests may be conducted at the investigator’s discretion. See Section 8.3.7.
Naso-pharyngeal swab			X											Can be before or after LY3819253 administration. For research purposes. See Section 8.3.7.
Nasal swab									X					For research purposes. This swab may be taken if a point-of-care test is done during the study, as described in Section 8.3.7.
Admission to study site		X												
Discharge from study site									X					
Physical examination Medical assessment	X	X	Pre-dose			X			X	As needed			X	Full PE/MA at screening and Visit 6/ED. Symptom-directed PE/MA at all other indicated time points and as deemed necessary by the investigator or designee.

Procedure / Assessments	Screening	Treatment Period								Follow-up Visits				Comment
Visit Number	V1	V2								V3	V4	V5	V6/ ED	
Week(s)		0								2	4	8	12	
Study Day	-14 to -1	-1	1	2	3	4	5	6	7	15 ±2d	29 ±3d	60 ±3d	85 ±3d	
Vital signs: blood pressure, body temperature, pulse rate ^a	X	X	Predose	24 h (±2 h)		X			X	X	X	X	X	Vital signs should be taken following at least 5-min rest in a supine position. Vital signs may be taken any time prior to dosing. If screening takes place on Day -1, there is no need to take vital signs twice on Day -1.
Single 12-lead ECG	X													
Concomitant medications review	X	X								X	X	X	X	
AE review	X	X	Predose	X	X	X	X	X	X	X	X	X	X	AEs to be reviewed only after participant has signed the study ICF.
HIV, hepatitis B/C serology	X													

Procedure / Assessments	Screening	Treatment Period								Follow-up Visits				Comment
Visit Number	V1	V2								V3	V4	V5	V6/ED	
Week(s)		0								2	4	8	12	
Study Day	-14 to -1	-1	1	2	3	4	5	6	7	15 ±2d	29 ±3d	60 ±3d	85 ±3d	
Pregnancy test (women only) ^b	X	X											X	Serum pregnancy test at screening, urine test at other timepoints. Day -1 urine test refers to test at admission; this is not needed if admissions is on the same day as screening. Postdose urine test(s) can be performed at the judgment of the investigator, if pregnancy is suspected.
Clinical laboratory tests ^a	X	X							X	X	X	X	X	Fasting is not required for these tests. If screening takes place on Day -1, there is no need to conduct these tests twice on Day -1.
Breath or urine ethanol screen		X												Ethanol screen may be repeated at other time points at the discretion of the investigator.
Urine drug screen	X	X												Day -1 urine test refers to test at admission; this is not needed if admission occurs on the same day as screening. Drug screen may be repeated at other time points at the discretion of the investigator.

Procedure / Assessments	Screening	Treatment Period								Follow-up Visits				Comment
	Visit Number	V1	V2								V3	V4	V5	
Week(s)		0								2	4	8	12	
Study Day	-14 to -1	-1	1	2	3	4	5	6	7	15 ±2d	29 ±3d	60 ±3d	85 ±3d	
SC LY3819253 or placebo dosing			X											
LY3819253 PK sampling ^a			X	X	X	X	X	X	X	X	X	X	X	Day 1 collection should be taken up to 4h postdose ±4h. The exact time of draw must be recorded. For Day 2 onwards, PK samples may be taken at any time after vital signs.
Injection site assessments			Predose; 1min ±1min, 10min ±2min, 30min ±5min, 240min ± 10min	24h ±4h	X	X	X	X	X	X	X	X	X	Timepoints include ISR assessment, VAS, if pain is reported, and the exploratory Scarletred tool. Scarletred timing is flexible and not confined to the windows shown, except for predose. See Section 8.2.5 for detail.
Immunogenicity			Predose							X	X	X	X	
Serum sample for exploratory biomarkers ^a			Predose		X					X	X	X	X	
Pharmacogenetics sample ^a			Predose											For storage only.

Abbreviations: AE = adverse event; COVID-19 = Coronavirus disease-2019; ECG = electrocardiogram; ED = early discontinuation; h = hours; HIV = human immunodeficiency viruses; I/E = inclusion/exclusion; ICF = informed consent form; MA = medical assessment; ISR = injection site reaction; min = minutes; PE = physical examination; PK = pharmacokinetics; SARS-CoV-2 = severe acute respiratory syndrome coronavirus 2; SC = subcutaneous; V = visit; VAS = visual analog scale.

- a When conducted on the same day, the order of procedures should be vital signs, ECG, and then blood sampling.
- b For women who are considered to be postmenopausal, follicle-stimulating hormone should be drawn to confirm postmenopausal status if necessary, according to Appendix 4 (Section [10.4](#)).

2. Introduction

2.1. Study Rationale

The clinical program for LY3819253 so far has involved IV dosing of LY3819253.

Study PYAG, will investigate SC dosing of LY3819253. Single SC doses of LY3819253, 350 mg and 700 mg, will be administered to establish the PK, safety, and tolerability profiles in healthy participants.

2.2. Background

The efficient community spread of SARS-CoV-2 has resulted in the current pandemic of COVID-19. There are no approved therapies to date for the treatment of COVID-19; Remdesivir is available under an emergency use authorization in the US (Gilead Sciences 2020).

SARS-CoV-2 gains entry to cells through binding of the spike protein to angiotensin-converting enzyme 2 receptors on cells (Hoffmann et al. 2020). LY3819253 is a neutralizing immunoglobulin G1 mAb to the spike protein of SARS-CoV-2. It is designed to block viral attachment and entry into human cells, and to neutralize the virus.

2.2.1. Summary Information from LY3819253 Program to Date

Additional information can be found in the IB.

2.2.1.1. Safety

The following blinded summaries of safety are as of 24 July 2020.

LY3819253 has been administered to humans in 2 clinical studies, Study PYAA and Study PYAB.

No SAEs or deaths have been recorded to date in either study.

Study PYAA

The first 3 cohorts of Study PYAA each consisted of 8 hospitalized participants with moderate or severe COVID-19 who were randomized to receive either a single IV dose of LY3819253 or placebo at a ratio of 6:2. The dose range was 700 mg to 7000 mg.

Sixteen out of 24 participants dosed with LY3819253 (across all doses) or placebo experienced at least 1 TEAE. Most TEAEs reported were mild to moderate severity. There have been no dose-limiting safety issues identified.

No AEs of infusion-related reaction have been reported.

Study PYAB

Enrollment is open for 700-mg (or placebo), 2800-mg, and 7000-mg cohorts. The treatment-group assignment for each participant remains blinded since the study is ongoing.

Eighty-eight participants have been administered LY3819253 or placebo. There have been 4 infusion reactions reported to date. Based on conversations with the site, these occurred within

approximately 30 minutes after the infusion was started, and were considered related to study treatment.

2.2.1.2. Pharmacokinetics

Preliminary data in a limited number of subjects suggest the PK profile of LY3819253 is consistent with the PK model-predicted profile and dose proportional following a single IV dose of 700 mg up to 7000 mg. Pharmacokinetic model-estimated IV clearance and half-life approximately 0.3 L/day and 2 to 4 weeks, respectively.

2.3. Benefit/Risk Assessment

Anticipated risk is considered low and is based on the known mechanism of action for human derived neutralizing antibodies in acute viral disease states. LY3819253 consists of a highly specific mAb directed at foreign (non-human) epitope(s). The complementarity determining regions of the mAb were derived from B lymphocytes of a convalescent SARS-CoV-2-infected patient; and, thus, have undergone natural positive and negative selection pressures in vivo, unlike humanized antibodies generated in mice. Therefore, off-target binding and tissue cross-reactivity are considered unlikely.

Nonclinical safety studies conducted to date using the IV route of administration have not demonstrated safety concerns. Toxicity studies supporting LY3819253 clinical trials consist of a tissue cross reactivity study, a 21-day rat toxicity study (IV administration), and an evaluation of ADE in vitro and in African green monkeys. Tissue cross-reactivity data did not suggest off-target binding of clinical relevance and supports use of the rat as the nonclinical safety model. The treatment phase of the 21-day repeat-dose toxicity study in rats, including histopathology evaluation, is complete and did not demonstrate adverse findings. Lastly, no evidence for ADE was observed in vitro or in nonhuman primates.

The maximum planned dose of LY3819253 in this study is 700 mg SC. This is lower than the maximum dose delivered IV in previous studies.

A theoretical risk is that LY3819253 may cause ADE of viral replication. This is based on responses observed to some mAb therapies used in other unrelated viral diseases. Unlike ADE associated with Dengue and Zika virus infections, this phenomenon has not been clearly established for coronavirus infections, and has not been reported to date with SARS-CoV-2. Additionally, limited experience with the use of convalescent serum as a treatment for patients with severe COVID-19 disease has not indicated safety concerns (Duan et al. 2020; Shen et al. 2020).

Additional manageable risks associated with most therapeutic monoclonal antibodies are the potential for hypersensitivity and cytokine release reactions. In addition, there is a potential for ISRs. Study participants will be in-house for the first 7 days after dosing, which will enable close monitoring for hypersensitivity reactions and ISRs post-injection.

Given the totality of data on LY3819253 and the well-established safety profile of other therapeutic monoclonal antibodies, the overall benefit/risk assessment of this study is considered favorable.

More detailed information about the known and expected benefits and risks and reasonably expected AEs of LY3819253 may be found in the IB.

3. Objectives and Endpoints

Objectives	Endpoints
Primary	
To determine the PK of single SC doses of LY3819253 in healthy participants	AUC(0-∞)
Secondary	
To describe safety and tolerability following single SC doses of LY3819253 in healthy participants	Incidence of spontaneously reported AEs, TEAEs, and SAEs; vital signs; clinical laboratory results
Exploratory	
To assess ISRs following single SC doses of LY3819253 in healthy participants	Characterization and measurement of incidence and severity of ISRs (including injection site pain) using data collected from the ISR assessment, as well as the exploratory tool (Scarletred).
To determine the immunogenicity of LY3819253 following single SC doses in healthy participants.	Incidence of TEADA.

Abbreviations: AE = adverse event; AUC(0-∞) = area under the concentration versus time curve from time 0 to infinity; ISR = injection site reaction; PK = pharmacokinetics; SAE = serious adverse event; SC = subcutaneous; TEADA = treatment-emergent antidrug antibodies; TEAE = treatment-emergent adverse event.

4. Study Design

4.1. Overall Design

This is a single-site study in healthy participants who will receive a single SC dose of LY3819253. The study will be participant- and investigator-blinded, randomized, and placebo controlled.

4.1.1. Screening and enrollment

Up to 3 cohorts may be enrolled. In Cohorts 1 and 2, there will be at least 9 participants per cohort (7 LY3819253:2 placebo), with the intention that at least 6 participants randomized to LY3819253 have sufficient evaluable data in each cohort.

For the optional Cohort 3, up to 9 participants will be enrolled and the cohort may be closed when at least 5 participants have been randomized to LY3819253. The number of participants and the ratio of LY3819253 to placebo may change based on enrollment numbers. However, the number assigned to LY3819253 will not exceed 7, and the number assigned to placebo will not exceed 2.

Participants will be screened within 14 days prior to Day 1 of dosing for each cohort. Participants will be admitted to the CRU as part of an inpatient visit on Day -1 and will be sequentially enrolled and then randomized to treatment.

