4.2. Scientific Rationale for Study Design

This is the first study to evaluate a new formulation via SC route of administration in humans. This study will be conducted with healthy participants, rather than patients with COVID-19, because the important biopharmaceutic questions related to the new SC route of administration, such as PK and tolerability, will be more efficiently investigated in the healthy human population.

The 4-day safety review together with in-patient status after dosing is sufficient to detect an acute adverse systemic response that would preclude dose escalation.

Placebo will be used as a comparator to allow interpretation of safety and tolerability data following administration of LY3819253.

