5.2 Screening and Enrollment

Up to 3 cohorts may be enrolled with at least 9 participants per cohort (7 LY3819253: 2 placebo), with the intention that at least 6 participants randomized to LY3819253 have sufficient evaluable data in each cohort.

Participants will be screened within 14 days prior to Day 1 of dosing for each cohort. Participants will be admitted to the clinical research unit (CRU) as part of an inpatient visit on Day -1 and will be sequentially enrolled and then randomized to treatment.

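### Cohort 3 has no placebo minimum, so it can close with no placebo participant, and closure at 5 would show that all five received LY3819253

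*Protocol*

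**What the plan says.** Protocol 4.1.1 treats the optional third cohort differently from the first two.

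- Cohorts 1 and 2: "In Cohorts 1 and 2, there will be at least 9 participants per cohort (7 LY3819253:2 placebo".
- Cohort 3, size and closure: a maximum of 9 participants, and "the cohort may be closed when at least 5 participants have been randomized to LY3819253".
- Cohort 3, flexibility: "The number of participants and the ratio of LY3819253 to placebo may change based on enrollment numbers".
- Cohort 3, limits: "the number assigned to LY3819253 will not exceed 7, and the number assigned to placebo will not exceed 2". Both limits are maxima.

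The note to the schema (Protocol 1.2) agrees: "The LY:PBO ratio for the optional Cohort 3 is an intention and may change subject to enrollment numbers".

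Participants are enrolled one after another and then randomized (4.1.1). Protocol 6.3 leaves the randomization tables to the statistician, states no block structure, and refers to a separate Blinding Plan. Protocol 4.1 describes the whole study as randomized and placebo-controlled, with participants and investigator blinded, and makes no exception for Cohort 3. Protocol 4.2 gives the purpose of placebo: "Placebo will be used as a comparator to allow interpretation of safety and tolerability data following administration of LY3819253".

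The SAP differs. Section 5.2 reads "Up to 3 cohorts may be enrolled with at least 9 participants per cohort (7 LY3819253: 2 placebo", which covers all three cohorts. SAP 6 reports placebo as one treatment group across cohorts.

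**The concern.** Permission to close Cohort 3 depends on how many participants have been allocated to LY3819253, and nothing guarantees that anyone in the cohort receives placebo. Two consequences follow.

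First, the cohort can end with no concurrent control. Cohort 3 gives the same planned 700 mg dose as Cohort 2 in different injection volumes (Protocol 6.1.1), so local tolerability of that injection scheme is a natural thing to read from it.

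Second, if the cohort closes under this rule with 5 participants, anyone who knows the rule and the total knows that all five received LY3819253. Injection-site assessments, with a pain VAS where pain is reported, continue to Day 85 (Protocol 1.3). The investigator's judgment of adverse-event relatedness is also tabulated (Protocol 9.4.3.1, SAP 9.4.1). These are the assessments most open to influence from knowing the treatment.

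**Working it through.** **The plan's own figure.** The only sample-size figure is the roughly 70% chance in Protocol 9.2, for 6 active participants per cohort and a 40% CV. The formula is P(t(0.95, n−1)·s/√n ≤ −ln 0.7), with s² distributed as σ²χ²(n−1)/(n−1). With n = 6 it gives 68.1% for σ = 0.40 and 72.5% for σ = √ln(1 + 0.4²) = 0.385. The stated figure is reproduced. It plays no part in what follows.

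**Inputs from Protocol 4.1.1 for Cohort 3.** Total at most 9; LY3819253 at least 5 at closure and at most 7; placebo 0 to 2.

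**Step 1: splits that comply at each closing total.**

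| Total at closure | Possible LY3819253:placebo splits |
|---|---|
| 5 | 5:0 |
| 6 | 5:1, 6:0 |
| 7 | 5:2, 6:1, 7:0 |
| 8 | 6:2, 7:1 |
| 9 | 7:2 |

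A cohort without placebo is allowed at totals of 5, 6 and 7. The total fixes the split only at 5 and at 9, and 7:2 is the ratio already published for Cohorts 1 and 2.

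**Step 2: chance of no placebo if closed at the fifth LY3819253 allocation.** The list structure is not given, so assume a nine-slot list with 7 LY3819253 and 2 placebo in random order. There are C(9,2) = 36 equally likely placements of the two placebo slots.

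- No placebo (closes at 5): both placebo slots lie in positions 6 to 9, C(4,2) = 6, so 6/36 = 16.7%.
- One placebo (closes at 6): one slot in positions 1 to 5 and one in 7 to 9, 5 × 3 = 15, so 15/36 = 41.7%.
- Two placebo (closes at 7): both slots in positions 1 to 6, C(6,2) = 15, so 15/36 = 41.7%.

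Mean enrolment at closure is (5×6 + 6×15 + 7×15)/36 = 225/36 = 6.25.

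**Step 3: other assumptions.** On the same list, closure at the k-th LY3819253 allocation leaves no placebo with probability C(7,k)/C(9,k).

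| Assumption | Chance of no placebo |
|---|---|
| Nine-slot list, close at 5th | 21/126 = 16.7% |
| Nine-slot list, close at 6th | 7/84 = 8.3% |
| Nine-slot list, close at 7th | 1/36 = 2.8% |
| Simple randomization at 7/9, close at 5th | (7/9)^5 = 28.5% |

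**Step 4: what remains as comparator.** At 7:2, Cohorts 1 and 2 supply 2 + 2 = 4 placebo participants to the SAP's pooled group. If each received the injection volumes of their own cohort, which the documents do not state outright, none received the Cohort 3 scheme.

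**The case against.** The case for leaving the plan alone has weight.

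- **Closure is optional and 5 is a floor.** A reader might infer that the closing total always reveals the split: 5 means no placebo, 6 means one, 7 means two. That would need closure at exactly the fifth LY3819253 allocation every time, which the text does not say. This objection stands, as the table of splits shows.
- **Knowing the split is not unblinding.** The 7:2 ratio of Cohorts 1 and 2 is openly stated. Individual assignments become known only when it is known that nobody is on placebo. This also stands, and it confines the blinding problem to closure at 5.
- **Placebo is pooled.** A reader might infer that the rationale in Protocol 4.2 fails for Cohort 3. SAP 6 keeps a placebo group from the other cohorts, so the rationale is weakened, not void. That group is not concurrent and does nothing for the blind.
- **The Blinding Plan is separate and not available here.** The documents do not say who closes the cohort, what blinded staff are told, or how much injection-site data is recorded before closure is known. It is therefore not established that every participant and assessor would learn the assignment. But a single site can count its own enrolment, and no blinding plan can supply a missing placebo participant.
- **The relaxed numbers were deliberate and the stakes are limited.** The protocol's summary of changes explains that Cohort 3 has no safety review leading to a further cohort, and so needs no minimum numbers. Injection-site reactions are exploratory, and SAP 9.4.11 plans no inferential safety analysis. That limits the importance. The stated reason, however, does not address a placebo minimum or the blind.

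**Conclusion.** The point holds in a limited form. Following Protocol 4.1.1 as written can leave Cohort 3 without any placebo participant. The chance is about 1 in 6 on a nine-slot 7:2 list closed at the fifth LY3819253 allocation. It ranges from 2.8% to 28.5% over the alternatives examined. All these figures rest on an assumed list structure and an assumed closing point, since the documents fix neither.

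Any closure without placebo removes the concurrent control for this injection scheme and leaves only pooled placebo from Cohorts 1 and 2. Closure at 5 also exposes the injection-site, pain and relatedness assessments to a lost blind. At 6 to 8 the total narrows the split without fixing it. The primary endpoint, AUC(0-∞), is a serum measure and is unaffected. The change is worth making because it is cheap; the flaw does not threaten the study's main result.

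**What to change.** 1. Keep the maximum of 7 LY3819253 and 2 placebo, and generate the Cohort 3 list as a first block of 6 (5 LY3819253:1 placebo) followed by a block of 3 (2:1).
2. In Protocol 4.1.1, replace the closing condition with a count of participants: the cohort may be closed once 6 participants have been randomized, with at least 1 of them on placebo.
3. Qualify the sentence in 4.1.1 that lets the number and ratio change, and the schema note in 1.2, so that neither can override the placebo minimum.
4. Reconcile SAP 5.2 with Protocol 4.1.1. The SAP still has at least 9 participants at 7:2 in every cohort, whereas the protocol has up to 9 in Cohort 3.

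Any closure at 6 or later then has at least 5 LY3819253 and at least 1 concurrent placebo participant, and the trigger no longer depends on a hidden allocation. Closure at 6 would imply a 5:1 split, but not who received placebo.

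The cost is a short edit in each of three places (Protocol 4.1.1, the schema note and SAP 5.2) and a blocked list. Against closing at the fifth LY3819253 allocation on the assumed nine-slot list, the smallest permitted closure takes 6 participants, compared with a mean of 6.25 and a maximum of 7. What is lost is the option of closing at 5, which on that list would arise 1 time in 6.
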